14.2.1 Primary Efficacy Analysis

The primary efficacy endpoint is the change from baseline in AGV at the 12-month time point. For a given interval [Date1, Date2], the AGV is defined as follows:

$$AGV = \frac{\text{StandingHeight at Date2} - \text{StandingHeight at Date1}}{\text{Interval Length (Days)}} \times 365.25$$

where the interval length in days is calculated as Date2 – Date1. AGV will be calculated for the following visits/intervals:

	Study 111-301 Amendment 4	Page 104
---	---------------------------	----------

- Baseline: [Date of last height measurement in study 901 at least 6 months prior to Date of Day 1 visit in study 301, Date of Day 1]
- Week 13: [Date of Day 1, Date of Week 13]
- Week 26: [Date of Day 1, Date of Week 26]
- Week 39: [Date of Day 1, Date of Week 39]
- Week 52 (12-month): [Date of Day 1, Date of Week 52]

The baseline of the AGV is established in the natural history study of Study111-901, based on the standing height measurements in the last 6 months prior to enrollment to Study 111-301.

The primary estimand is the difference in mean change from baseline in AGV at 12-month time point between the BMN 111 group and the placebo group. The estimand is defined on all randomized subjects who received at least one dose of double-blinded BMN 111 or placebo. The least-squares (LS) means of the change from baseline in AGV at 12-month will be used to estimate the primary estimand for the BMN 111 group and the placebo group based on an analysis of covariance (ANCOVA) model, with fixed-effect terms including treatment group, sex, and Tanner stage, and age and the baseline AGV as covariates. The following primary hypothesis will be tested (two-tailed):

H₀: Difference in mean AGV change from baseline at 12 months between BMN 111 group and the placebo group = 0

H_a: Difference in mean AGV change from baseline at 12 months between BMN 111 group and the placebo group ≠ 0

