4.2 Study Design

Study 111-301 is a Phase 3 randomized, placebo-controlled, double-blind multicenter study to evaluate the effect of BMN 111 on growth in children with ACH. Subjects who are 5 to < 18 years old with documented ACH confirmed by genetic testing will have been enrolled in Study 111-901 (observational run-in study in pediatric patients with ACH) for at least a 6-month period immediately before study entry, and meet all study eligibility criteria.

Subjects who discontinue from the study drug will be encouraged to remain in the study and continue to undergo as many of the protocol-specified procedures and assessments as possible for the remainder of the study, as long as such continued participation does not detrimentally affect the health, safety, or welfare of the subject.

[figure not shown]
This 60-week study (up to 4 weeks of screening, 52 weeks of treatment with an additional 4 weeks of safety follow up) allows for assessment of the effect of daily BMN 111 administration on change from baseline in AGV, height, and body proportions in subjects treated with BMN 111 compared with control subjects in the placebo group. In addition, this study will help to further characterize safety and tolerability of BMN 111 in children with ACH.

At least 110 eligible subjects will be stratified based on sex and Tanner stage (Stage I, and > Stage I, with no more than 20% of subjects > Tanner Stage I) at Screening, and randomly assigned in a 1:1 ratio to one of two treatment groups: placebo or BMN 111 at 15 µg/kg. Approximately 33 clinical centers worldwide will participate in the study.

The 111-301 study design is presented below.

	Study 111-301 Statistical Analysis Plan
---	--

Figure 4.2.1: Study Design

Subjects who complete the 52 week treatment period in 111-301 study on randomized treatment, will be eligible to receive open label BMN 111 15 µg/kg daily in 111-302, to assess safety and efficacy of BMN 111 over the longer term. Subjects will have the option to enroll in 111-302 after the Week 52/Study Completion Visit. Week 52 assessments will serve as Baseline assessments for entry to study 111-302 if the visit occurs on the same day or within 2 weeks. Subjects who enroll into 111-302 more than 2 weeks after the 111-301 Week 52 visit will have a separate Baseline visit; the same assessments as those performed at Week 52 will be repeated at that time.

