**Study 111-301 Statistical Analysis Plan**

- Week 52 (111-301).

Each table will include summaries of the absolute measures at each of these time points, and change from baseline at Week 26 and Week 52 (applying visit windows). The tables will summarize data by treatment group. These summaries are on continuous data and will include the number of subjects with assessments, mean, SD, median, 25th and 75th percentile, minimum and maximum.

Results of the statistical analyses will be provided in separate tables, including the least-squares (LS) mean change from baseline at Week 52 for each treatment group, the treatment difference in LS means (calculated as BMN 111 – Placebo), the 95% confidence interval (CI) for the treatment difference, and corresponding 2-sided p-value.

ANCOVA models will be used to determine the treatment difference at 52 weeks. Unless otherwise specified, all models include the following baseline covariates:

- Treatment group
- Stratum: (Male Tanner Stage I, Female Tanner Stage I, Male Tanner Stage >I, Female Tanner Stage >I)
- Age at baseline
- AGV at baseline
- Height Z-score at baseline

Note: If a subject is incorrectly assigned to a stratum at the time of randomization, they will be analyzed according to their actual sex and Tanner stage.

Subgroup analyses will only be performed for the primary analyses of the primary and key secondary endpoints (see Section 14.7).

PI will include the mean values used in analyses and summaries, and will be ordered by treatment group, subject and visit date. An additional PI of standing height will include all assessments (i.e., individual measures and means of the measures).

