Each of the 10 imputed datasets will be analyzed using an ANCOVA model that includes the following fixed-effect terms:

- Treatment group
- Stratum (Male Tanner Stage I, Female Tanner Stage I, Male Tanner Stage >I, Female Tanner Stage >I)

Study 111-301 Statistical Analysis Plan

- Baseline age
- Baseline AGV
- Baseline height Z-score

SAS PROC MIXED will be used to perform the analysis.

PROC MIXED;

CLASS Stratum Treatment;

MODEL Change from baseline in AGV at Week 52 = Baseline_Age Baseline_AGV
Baseline_Height_Z-Score Treatment Stratum;

LSMEANS Treatment / DIFF = control (“Placebo”) CL;

RUN;

For each imputed dataset, PROC MIXED will generate the least-squares (LS) mean change from baseline in AGV at Week 52 for each treatment group, along with the difference in LS means (calculated as BMN 111 – Placebo). PROC MIANALYZE will then be used to combine all of the estimates across the 10 imputed datasets in order to generate an overall estimate for each treatment group, and for the difference between treatment groups, with a 95% confidence interval for the difference and 2-sided p-value. The study will be considered positive if the 2-sided p-value in favor of BMN 111 is <0.05.

If there are less than 5 subjects with reference data as defined above then missing standing height at Week 52 (i.e. Day 365) will be imputed by applying the baseline AGV (cm/yr) to the last available height assessment as follows:

Standing Height at Day 365 =

$$\text{Last Assessed Height} + \frac{\text{AGV at Baseline}}{365.25} \times (365 - \text{Study Day of Last Height Assessment})$$

Based on this imputed standing height, the height z-score and AGV at Week 52 will be calculated. The ANCOVA model will then be applied to AGV at Week 52.

In the event that there are no subjects who discontinue treatment early with a missing assessment at Week 52 the ANCOVA model will be applied without any imputation.

This ANCOVA model analysis without imputation will be repeated on the PP population.

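### The arm-level LS means give Tanner >I children half the weight although they are capped at 20% of enrolment; the treatment difference is unaffected

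*SAP*

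**What the plan says.** The primary model in SAP 14.3.2 declares "CLASS Stratum Treatment" and ends its list of effects with "Baseline_Height_Z-Score Treatment Stratum". Stratum is therefore a categorical main effect, and no treatment-by-stratum term is fitted. Its levels are "Stratum (Male Tanner Stage I, Female Tanner Stage I, Male Tanner Stage >I, Female Tanner Stage >I"). The LS means request is "LSMEANS Treatment / DIFF = control", followed by confidence limits. Neither that section nor the rest of the SAP states a weighting.

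Arm-level results are planned outputs. SAP 14.3.2 combines the imputed datasets to "generate an overall estimate for each treatment group, and for the difference between treatment groups". SAP 14.1 puts the "least-squares (LS) mean change from baseline at Week 52 for each treatment group" in the results tables. The LS means requests for height Z-score (14.4.1), upper:lower segment ratio (14.4.2), body proportion ratios (14.5.1) and growth measures (14.5.2) also give no weighting.

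SAP 4.2 limits enrolment, "with no more than 20% of subjects > Tanner Stage I". The estimand in SAP 14.3.2 has the FAS as its population and the difference between arms as its summary. Protocol 14.2.1 says "The least-squares (LS) means of the change from baseline in AGV at 12-month will be used to estimate the primary estimand" and refers there to each group.

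**The concern.** An LS mean for an arm is a prediction at a chosen mix of the categorical effects and at the overall means of the covariates. When no option is given, the mix is equal over the class levels. With two of four strata at Tanner >I, the prediction is for a group that is half Tanner >I, held at the whole-trial average age, baseline AGV and height Z-score. At least 80% of the enrolled children are Tanner I.

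A reader asking how much growth velocity changed on BMN 111, or on placebo, will take the arm LS mean as describing the enrolled children. If Tanner stage still predicts the change after adjustment, the arm LS means will be offset from the enrolled-mix values, and the plan gives no explanation. They are also less precise, because half the weight sits on the smallest strata.

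**Working it through.** **Inputs.** 55 per arm, a difference of 1.75 cm/yr, SD 2.80 and about 90% power (Protocol 14.6, SAP 4.5); 1:1 allocation and the 20% cap (SAP 4.2); four strata and a main-effects model (SAP 14.3.2). Assumed: strata balanced between arms, sexes 50:50, and 2.80 as the residual SD.

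**Plan's own figure.** 1.75 / (2.80 × √(2/55)) = 3.28. Two-sided power at 0.05 is 90.1% by noncentral t on 108 df and 90.6% by normal approximation, so the stated power reproduces. It is not in dispute; its inputs give the scale here.

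**Weights.** Equal weighting gives Tanner >I 2 × 1/4 = 50%. Enrolment gives at most 20% (22 of 110). The over-weighting is 0.50/0.20 = 2.5-fold at the cap and 0.50/0.10 = 5-fold at a 10% share.

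**Shift in each arm mean** = (0.50 − share) × b, where b is the Tanner >I minus Tanner I coefficient adjusted for age, baseline AGV and height Z-score. The documents do not give b, so a range is assumed, in either direction:

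| Assumed b (cm/yr) | Shift at 20% share | Shift at 10% share |
|---|---|---|
| 0 | 0 | 0 |
| 0.5 | 0.15 | 0.20 |
| 1 | 0.30 | 0.40 |
| 2 | 0.60 | 0.80 |

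**Treatment difference.** Both arms' LS means use the same stratum weights and covariate values. Without an interaction these cancel, leaving the treatment coefficient whatever the weights.

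**Standard error of an arm mean.** In an additive model, stratum effects are estimated from both arms together. Before covariates, the variance is σ²[1/55 + Σ(0.25 − p_k)²/N_k], where p_k is the enrolled share of stratum k and N_k its size over both arms. With observed margins the second term vanishes. The SE ratio is √(1 + 55 × Σ(0.25 − p_k)²/N_k).

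- 20% share: p = 0.40, 0.40, 0.10, 0.10; N = 44, 44, 11, 11. Σ = 2 × 0.0225/44 + 2 × 0.0225/11 = 0.00511; ratio = √1.281 = 1.13.
- 10% share: p = 0.45, 0.45, 0.05, 0.05; N = 49.5, 49.5, 5.5, 5.5. Σ = 2 × 0.04/49.5 + 2 × 0.04/5.5 = 0.01616; ratio = √1.889 = 1.37.

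With σ = 2.80, the SE is 2.80/√55 = 0.38 cm/yr under observed margins, against 0.43 (20% share) and 0.52 (10% share) under equal weights.

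**Check with covariates.** The SAP model was fitted to one simulated trial at the cap (88 Tanner I, 22 Tanner >I, residual SD 2.80, assumed covariates). The fitted b was −0.997:

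| Weighting | Placebo mean | BMN 111 mean | Difference (SE) |
|---|---|---|---|
| Equal | −0.381 | 0.980 | 1.361 (0.549) |
| Observed margins | −0.082 | 1.279 | 1.361 (0.549) |

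Both arms move by −0.299 = 0.30 × (−0.997), and the difference and its SE do not move. Over 500 such trials the SE ratio for the BMN 111 mean averaged 1.26. That is above 1.13 because the simulated Tanner >I children were assumed to be older (10.5 to 15 years against 5 to 11.5).

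**The case against.** The strongest reply is that nothing confirmatory is at stake. The estimand's summary is the difference between arms, success is judged on that p-value, and the gatekeeping sequence uses differences only. That stands in full. A reader might infer from the over-weighting that the treatment effect or its test is biased; the main-effects model rules this out. Nor does the protocol's mention of LS means by group make the arm means the estimand, because the same paragraph defines the estimand as a difference.

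Second, equal weighting is the standard LS-mean definition. That is also true: it is a convention, not a coding error, and an option in the final program may already change it. The four-level coding is not the cause either, since the protocol's separate sex and Tanner terms would give the same 50%.

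Third, the SAP also tabulates observed change by arm (14.3.1, 14.1), subject counts per stratum (5.1), and differences by Tanner stage and stratum (14.7). This helps the reader, but it does not correct the adjusted arm means.

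Fourth, the size of the shift rests on an assumed coefficient. That stands. After adjustment for age, AGV and height Z-score, the coefficient could be near zero.

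A reader might also compute the loss of precision within each arm, as √Σ(0.25²/n_k) ÷ √(1/55), and obtain 1.25 at a 20% share and 1.67 at 10%. That formula estimates stratum means separately by arm, which implies an interaction the SAP does not fit. A ratio near 1.25 at the cap can arise with covariates, but only if age is assumed to be strongly related to Tanner stage, and the documents give no such correlation.

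**Conclusion.** The point holds for the arm-level LS means only. As written, they describe an equal mix of the four strata, with Tanner >I at 50% against an enrolled maximum of 20%. The shift is 0.30 × the adjusted Tanner coefficient at the cap: 0.15 to 0.60 cm/yr for an assumed coefficient of 0.5 to 2 cm/yr, equal in both arms, and zero if the coefficient is zero. For height Z-score and the ratios the same formula applies in their own units, but the documents give nothing from which to size it. The arm-mean SE is about 13% larger at a 20% share and 37% larger at 10% before covariates, and more if age tracks Tanner stage.

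These figures assume the default LSMEANS weighting, balanced strata and a 50:50 sex split. The treatment difference, its CI, its p-value and the testing sequence do not change. This is a reporting improvement of low severity.

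**What to change.** Add the OM (observed margins) option to the LSMEANS statements in SAP section 14 that report arm means: 14.3.2, 14.4.1, 14.4.2, 14.5.1 and 14.5.2. Take the margins from the dataset being analysed, with both arms pooled: the FAS for the primary and key secondary analyses, and the PP or observed-data set where those are analysed. FAS margins should not be imposed on every dataset. The subgroup forest plots in 14.7 report differences only and need no change.

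The cost is one option per statement and a sentence in SAP 14.1, with no effect on any difference, interval or p-value. Fixing it before unblinding avoids a later choice between two sets of arm means. If the code is to stay as it is, a table footnote would serve as a lesser remedy: it should say that arm LS means weight the four strata equally and that only the difference is to be interpreted.

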**Study 111-301 Statistical Analysis Plan****14.3.3 Sensitivity and Supplementary Analyses Defined for AGV**

The following sensitivity and supplementary analyses are proposed for assessing the robustness of the results of the primary analysis. All visits referred to in the analyses, are based on the analysis windows described in Section 5.4. Summary tables for the models and descriptive summary statistics tables will be provided for each sensitivity analysis.

Sensitivity Analysis: Washout model where missing data for an endpoint for both treatment groups will be imputed using data from the placebo arm.

This approach addresses the same estimand as the primary analysis but with an alternative estimator. Employing this model, any potential BMN 111 treatment effect in those patients in the BMN 111 active group who are off-treatment will be washed out. Specifically, for the washout imputation, the missing data in an endpoint for both treatment groups will be imputed using observed endpoint data from the placebo arm.

PROC MI will be used to impute the missing standing height assessments at Week 52, as described for the primary analysis. However, for this analysis, according to the washout specifications, only placebo data (including off treatment assessments) will be used in the missing not at random (MNAR) option to implement the control-based pattern imputation. Therefore, for the subjects in the BMN 111 active treatment group, no observed post baseline assessments will be considered in the imputation process.

Supplementary Analysis 1: ANCOVA model on completers.

This approach addresses the same estimand as the primary analysis, except that the intercurrent event is defined as subject discontinuation from the study. In this analysis, the estimator will be the difference between the two randomized groups in the mean change from baseline in AGV at Week 52, observed from subjects who have non-missing AGV observation at 52 weeks. The LS means of the change from baseline in AGV at 52 weeks will be estimated for both the randomized groups by applying the ANCOVA model without multiple imputation described in the primary analysis. In this analysis, only subjects with observed AGV change from baseline at 52 weeks will be included. No imputation will be performed for missing 52-week standing height measurements.

Supplementary Analysis 2: ANCOVA model excluding assessments that occur post either limb lengthening or growth hormone/gonadotropin-releasing hormone.

This approach addresses the same estimand as the primary analysis except that the intercurrent event, defined as rescue treatment for achondroplasia, is handled differently. In the event that a subject has been receiving rescue medication from the start of the study, they

Study 111-301 Statistical Analysis Plan

will be excluded from this supplementary analysis. The analysis will be conducted on imputed data, as described for the primary analysis; however, any assessments that are measured following either limb lengthening or growth hormone/ gonadotropin-releasing hormone will be excluded from this analysis. The ANCOVA model described in the primary analysis will be applied, and the estimator will be the difference between the two randomized groups in the mean change from baseline in AGV at Week 52.

14.4 Key Secondary Efficacy Endpoint(s)

The two secondary efficacy endpoints with confirmatory testing (referred to in this document as “key secondary endpoints”) are the change from baseline at Week 52 in height Z-score and the change from baseline at Week 52 in upper to lower body segment ratio.

14.4.1 Height Z-Score

Standing height is measured at Screening, Day 1, Week 13, Week 26, Week 39, and Week 52. Each measurement of standing height will be converted to an age-and sex-appropriate standard deviation score (SDS), also referred to as a Z-score, by comparison with reference data available for average stature children from the Centers for Disease Control and Prevention (CDC).

The following key secondary hypothesis will be tested (two-tailed):

H₀: Difference in mean height Z-score change from baseline at week 52 between BMN 111 group and the placebo group = 0

H_a: Difference in mean height Z-score change from baseline at week 52 between BMN 111 group and the placebo group ≠ 0

Height Z-score will be analyzed using the same methods and estimand formulation as the primary analysis. If multiple imputation is applied for testing the primary endpoint then the null hypothesis of no difference between the BMN 111 group and the placebo group in the mean change from baseline in the height Z-score at the Week 52 time point will also be tested based on 10 imputed data sets. Missing height Z-score at Week 52 will be calculated from the imputed standing height at this visit, as described for the primary endpoint. If multiple imputation is not applied for the primary endpoint, then the Week 52 height Z-score will be imputed as described above in Section 14.3.2.

SAS PROC MIXED will be used to test the null hypothesis using an ANCOVA model described below.

Study 111-301 Statistical Analysis Plan

PROC MIXED;

CLASS Stratum Treatment;

MODEL Change from baseline in Height Z-score at Week 52 = Baseline_Age
Baseline_AGV Baseline_Height_Z-score Treatment Stratum;

LSMEANS Treatment / DIFF= control (“Placebo”) CL;

RUN;

The least-squares (LS) mean change from baseline in height Z-score at Week 52 will be presented for each treatment group, along with the difference in LS means (calculated as BMN 111 – Placebo), the 95% confidence interval for the difference, and 2-sided p-value. In the event that the primary endpoint test is positive, the testing on the key secondary is considered to be confirmatory. The endpoint is considered positive if the 2-sided p-value in favor of BMN 111 is < 0.05.

This analysis will be repeated on the PP population, using the same approach as described for the primary endpoint. In addition, the sensitivity and supplementary analyses of height Z-score [described in section 14.3.3] will be performed using the FAS population.

Summary tables are provided as described in Section 14.1. In addition, a line plot of the mean (+/-SD) height Z-score will be presented for visits ≥ 12 Months Prior, ≥ 6 Months Prior, Baseline, Week 26 and Week 52 by treatment group.

Height Z-scores derived for all visits will be included in data listings.

14.4.2 Upper to Lower Body Segment Ratio

Standing height and sitting height are measured at Screening, Day 1, Week 13, Week 26, Week 39, and Week 52.

The upper to lower body segment ratio will be calculated at each visit as follows:

$$\text{Upper to Lower Body Segment Ratio} = \frac{\text{Sitting height}(cm)}{\text{Standing height}(cm) - \text{Sitting height}(cm)}$$

The upper to lower body segment ratio at Baseline, Week 26 and Week 52, and its change from baseline at Week 26 and Week 52 will be summarized (n, mean, SD, median, 25th and 75th percentile, minimum, maximum) and presented by treatment group. Figures will be provided as described in Section 14.1.

The following key secondary hypothesis will be tested (two-tailed):

Study 111-301 Statistical Analysis Plan

H₀: Difference in mean upper:lower body segment ratio change from baseline at week 52 between BMN 111 group and the placebo group = 0

H_a: Difference in mean upper:lower body segment ratio change from baseline at week 52 between BMN 111 group and the placebo group ≠ 0

The upper to lower body segment ratio will be analyzed using the same methods and estimand formulation as the primary analysis. The primary analysis of the upper to lower body segment ratio will be assessed on the FAS. If MI methods are used to impute Week 52 results for the primary endpoint (AGV), then the same MI approach will be used to impute missing Week 52 upper to lower body segment ratios. Missing sitting height at Week 52 will be imputed in the same manner as missing standing height, using PROC MI. Missing upper to lower body segment ratios Week 52 will be calculated from the imputed values for sitting and standing height. The difference between the BMN 111 group and the placebo group in the mean change from baseline in the upper:lower body segment ratio at Week 52 will be tested based on 10 imputed data sets.

If multiple imputation is not applied for the primary endpoint, then missing sitting height and standing height at Week 52 will be imputed by applying the baseline AGV for sitting height and standing height to the last available sitting/standing height assessment (as described in Section 14.3.2). Based on this imputed sitting height and standing height at Week 52, the upper:lower body segment ratio will be calculated, and the model described above will then be applied at Week 52.

SAS PROC MIXED will be used to test the null hypothesis using an ANCOVA model described below.

PROC MIXED;

CLASS Stratum Treatment;

MODEL Change from baseline in upper:lower body segment ratio at Week 52 =
Baseline_Upper:Lower Body_Segment_Ratio Baseline_Age Baseline_AGV
Baseline_Height_Z-score Treatment Stratum;

LSMEANS Treatment /DIFF = control (“Placebo”) CL;

RUN;

The least-squares (LS) mean change from baseline in upper to lower body segment ratio at Week 52 will be presented for each treatment group, along with the difference in LS means (calculated as BMN 111 – Placebo), the 95% confidence interval for the difference, and

